Following these initial screening studies, the patient will undergo a ^{129}Xe – MRI exam. The details of the ^{129}Xe MRI are as follows. The subject will be escorted to the MRI suite where they will be fitted with a ^{129}Xe transmit-receive vest coil. They will then be positioned supine on the scanner bed. They will be coached about how to inhale HP ^{129}Xe from the dose delivery bags. Then the subject and bed will be moved into the scanner and they will undergo basic ^1H localizer and anatomical scans. Once localization is complete, subjects will undergo several MRI scans after inhalation of HP ^{129}Xe . Each dose will be limited to a volume less than 25% of subject lung capacity (TLC) as is the case for all protocols currently carried out under IND 109,490. After each ^{129}Xe dose, the table will be moved out of the magnet bore and the subject queried for any symptoms. The next ^{129}Xe dose and scan will be administered when the subject and study personnel are ready. Subjects will undergo a ^{129}Xe dynamic spectroscopy and calibration, and ^{129}Xe gas exchange MRI. Any given ^{129}Xe MRI scan may be repeated, if necessary. After completing this sequence, the subject will get off the MRI table, rest for 5 minutes and then undergo the same scans to assess repeatability. There is no limit to the number of ^{129}Xe scans allowed during the session, although current ^{129}Xe production capabilities generally limit this to 5 ^{129}Xe doses. After completing the ^{129}Xe portion of the scan, the ^{129}Xe coil will be removed and patients fitted with a torso array ^1H coil. They will then undergo a free-breathing ultra-short-echo time ^1H MRI to delineate lung structure.

Following visit V1, the coordinator will ask the patient and/or contact the patient to confirm the start date of an FDA approved IPF therapies (pirfenidone and nintedanib). The decision of which type of therapy will be completely at the discretion of the patient and their primary pulmonologist but will be recorded by the coordinator. Following initiation of therapy, the subject will return for visits at 3 (V3), 6 (V4) and 12 (V5) months following initiation of therapy. At that time, the subjects will undergo a physical exam, spirometry and a 6MWD (only at screening visit, 3 month and 6 month visit) if not performed as a part of their usual care. At 6 months, the subjects will also undergo a HRCT scan. This will not

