7. Consent Process: The study coordinator will consent prospective participants. If necessary, the participants will have no less than 24 hrs to consider their participation. The consenting will take place in the private room or laboratory setting with closed doors. Only the coordinator and prospective participant will be in the room during the consent process. We will encourage potential subjects to ask questions and to take as much time as needed to consider participation. If the subject wishes to consider the study overnight or longer, an additional appointment will be made for the subject to continue the consent process. From the time of initial contact until the participant completes the study they will have a coordinator's contact information.

8. Subject's Capacity to Give Legally Effective Consent: Subjects without capacity to give consent will not be recruited into this study.

9. Study Interventions: Hyperpolarized xenon will be administered in multiple doses in volumes up to 25% of subject TLC followed by a breath hold of up to 15 seconds. Subsequent ¹²⁹Xe doses will only be administered once the subject is ready to proceed. Hyperpolarized ¹²⁹Xe MRI will be used to acquire one or all of the following data:

Pre- treatment (Study V1)

1. 3-Plane Localizer
2. ¹²⁹Xe dynamic spectroscopy and calibration to test coil tuning and loading in each subject to permit optimal setting of imaging parameters.
3. ¹²⁹Xe distribution dissolved in the pulmonary interstitial spaces and capillary blood as an indicator of pulmonary gas exchange.
4. Breath-hold 3D radial MRI to delineate the thoracic cavity
5. Subjects will dismount the MRI table, rest for 5 minutes
6. 3-Plane Localizer
7. ¹²⁹Xe dynamic spectroscopy and calibration to test coil tuning and loading in each subject to permit optimal setting of imaging parameters.
8. ¹²⁹Xe distribution dissolved in the pulmonary interstitial spaces and capillary blood as an indicator of pulmonary gas exchange.
9. Breath-hold 3D radial MRI to delineate the thoracic cavity

Using Xenon MRI to Evaluate the Efficacy of Therapies for Idiopathic Pulmonary Fibrosis

Post Treatment (V3, V4, and V5)

1. 3-Plane Localizer
2. ^{129}Xe dynamic spectroscopy and calibration to test coil tuning and loading in each subject to permit optimal setting of imaging parameters.
3. ^{129}Xe distribution dissolved in the pulmonary interstitial spaces and capillary blood as an indicator of pulmonary gas exchange.

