Although sensitivity to therapy response is expected to be highest for the imaging metrics, the study has been conservatively powered on the basis of the spectroscopic RBC:barrier ratio, which thus far, is most well-documented of the ¹²⁹Xe metrics in the literature. Early studies, which did not control carefully for lung inflation reported a variability of 6.6% in this metric. Moreover, a recent study of natural progression in a group of IPF patients (n=18, on a mix of treatments or untreated) revealed a decline in RBC:barrier of 20% in this metric over the course of 6 months. We assume that we will observe a smaller decline in RBC:barrier in our cohort, which will all receive treatment, and estimate that only a 10% decline will be observed at 12 months. Given this estimate of variability and effect size, and requiring 90% power, would be achieved with a sample of only 5 patients. Based on established patterns in our clinics, we expect roughly half the patients to receive pirfenidone with the other half receiving nintedanib. Assuming that one of the drugs reduces RBC:barrier decline to only 5% over 12 months, whereas the other yields a decline of 10%, would require a sample of 19 patients, which is just achievable with the sample of 20 patients expected to be enrolled.

Baseline Repeatability and Prespecified Futility Analysis – As this is a new clinical study with unknown efficacy in detection a preliminary analysis of the data will be performed. Following completion of the first 10 patients in the study the study team will perform an analysis for futility based on test – retest variability. Baseline repeatability of each of the ¹²⁹Xe metrics will be assessed using Bland- Altman plots, and a pairwise, two-tailed *t*-test will be used to check for significant differences. For each derived parameter, the coefficient of variation will be calculated. Our threshold to stop the study is if the RBC:Barrier ratio is outside of 95% CI on test-retest of $\pm 20\%$ of the dynamic range. We estimate the 95% confidence interval to be better than $\pm 10\%$ with this sample size.

Correlation between ¹²⁹Xe metrics, CT scores, and clinical tests will be evaluated using the Pearson correlation coefficient.

To measure changes from baseline, we will calculate the mean, standard deviation, median and range of each metric, and at each time point, the 95% confidence interval for means and averaged changes relative to baseline will be provided. Changes compared to

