Using Xenon MRI to Evaluate the Efficacy of Therapies for Idiopathic Pulmonary Fibrosis

baseline will be tested using the Wilcoxon Singed-Rank test. In all analyses, $P < 0.05$ (two-sided) will be considered the criterion for statistical significance. There will be no adjustment for multiple testing, because of the small number of hypothesis tests considered. The trajectory changes of these endpoints over time will be evaluated using linear models for repeated measures. Point estimates and confidence intervals for relevant parameters will be provided for descriptive purposes.

Baseline images will be analyzed for functional or structural indicators that may predict therapeutic response using mixed linear models. We will conduct this modeling, while considering differences in treatment group, clinical/demographic covariates (fixed effects), and subject (random effect). Diagnostic plots will be obtained to assess possible violations in model assumptions. All statistical analyses and graphics will be generated in R, or similar statistical package.

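### The claim of 90% power with 5 patients does not hold for the planned Wilcoxon signed-rank test, whose exact and continuity-corrected forms cannot reach two-sided P<0.05 at n=5

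*Combined protocol and SAP*

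**What the plan says.** Section 12 bases power on the spectroscopic RBC:barrier ratio and gives two inputs.

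- Variability: "Early studies, which did not control carefully for lung inflation reported a variability of 6.6% in this metric".
- Effect: the investigators "estimate that only a 10% decline will be observed at 12 months".

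From these it concludes that "requiring 90% power, would be achieved with a sample of only 5 patients". No test is named for that calculation.

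Later in Section 12, under the analysis of changes, the plan says that changes compared to "baseline will be tested using the Wilcoxon Singed-Rank test", and sets P<0.05, two-sided, as the significance criterion for all analyses. It does not say whether the exact test or a normal approximation will be used.

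Section 4 (Design and Procedures) plans 20 patients followed after starting therapy. It also describes a second xenon acquisition at V1, in which the patient will "rest for 5 minutes and then undergo the same scans to assess repeatability". Section 9 (Study Interventions) lists the repeat for V1 but not for the post-treatment visits V3, V4 and V5.

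**The concern.** A sample-size statement should describe the test that will be run. The signed-rank test has a discrete null distribution, and with very few patients its smallest attainable p-value can exceed the significance level. Five patients is such a case, so the stated 90% may have been carried over from a formula for a different test.

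The meaning of the 6.6% is a second difficulty. The plan calls it only a variability. If it is the SD of a single measurement, the SD of a within-patient change is larger and the required number rises further.

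This is one of only two power statements in the plan, and the section describes the powering as conservative. A reader could take 5 as an adequate minimum, for example if few patients return for the 12-month MRI.

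**Working it through.** **Inputs (all from Section 12, except the 20 patients, from Section 4).** Decline 10%; variability 6.6%; two-sided level 0.05; power 90%; Wilcoxon signed-rank test; 20 treated patients.

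**Step 1. Reproduce the plan's figure.** The one-sample normal formula with known SD is n = (z₀.₉₇₅ + z₀.₉₀)² × (SD/decline)².

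- With 6.6% as the SD of the change: (1.960 + 1.282)² × (6.6/10)² = 4.58, rounded up to 5. Power of this z-test at n=5 is 92.3%.
- With a 5-point difference: (1.960 + 1.282)² × (6.6/5)² = 18.3, rounded up to 19, which is the plan's other sample-size figure. This identifies the formula.

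The arithmetic is correct for a z-test.

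**Step 2. Smallest two-sided p-value of the signed-rank test at n=5.** The extreme result is all five changes in the same direction, with rank sum 15. Under the null the mean is 7.5 and the SD is √(5×6×11/24) = 3.708.

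- Exact: 2/2⁵ = 0.0625.
- Continuity-corrected: z = (15 − 7.5 − 0.5)/3.708 = 1.888, p = 0.059.
- Uncorrected: z = (15 − 7.5)/3.708 = 2.023, p = 0.043.

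The first two forms can never reject at 0.05, so their power is zero for any effect, SD or distribution.

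**Step 3. Power of the uncorrected form at n=5.** It rejects only when all five changes share a sign. For normal changes the power is Φ(10/SD)⁵, plus a negligible term for five increases.

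- SD 6.6%: Φ(1.515)⁵ = 0.935⁵ = 0.715.
- It reaches 90% only if the SD of the change is about 4.9% or less (0.901 at 4.90; 0.896 at 4.95).

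For comparison, a two-sided paired t-test with n=5 and SD 6.6% has 71.9% power and needs 7 patients for 90%.

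**Step 4. What the 6.6% could mean.** If it is the SD of one measurement and errors are independent (an assumption), the SD of the change is:

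- one baseline scan against one follow-up scan: 6.6 × √2 = 9.33%;
- mean of the two V1 scans against one follow-up scan: 6.6 × √(1 + 1/2) = 8.08%.

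**Step 5. Patients needed by the exact signed-rank test.** Simulated with normally distributed changes and a 10% decline.

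| SD of change | Power at n=5 | Last n below 90% | First n at or above 90% | Power at n=20 |
|---|---|---|---|---|
| 6.6% (6.6% is the SD of the change) | 0% | n=7: 89% | n=8: 92% | >99% |
| 8.1% (per measurement, V1 scans averaged) | 0% | n=9: 85% | n=10: 92% | >99% |
| 9.3% (per measurement, one baseline scan) | 0% | n=12: 89% | n=13: 93% | >99% |

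Twenty patients with a 12-month MRI keep 90% power up to an SD of the change of about 12.7% (90% at 12.7%; just under at 12.8%).

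**The case against.** The strongest reply is that nobody plans to analyse five patients. Section 4 plans 20 on therapy. Section 12 uses the 5 to show that an overall decline is easy to detect, then sets it beside the 19-patient drug comparison. The futility look uses 10 patients and a different criterion. That is right, and it limits the consequence to a wrong figure. It does not make the figure correct.

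It can also be said that the signed-rank test is not the only planned inference on change: Section 12 also plans confidence intervals for mean changes and linear models for repeated measures. This is true, but the signed-rank test is the one test named for change from baseline, and a paired t-test at n=5 also falls short at 71.9%.

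Nothing in the plan suggests averaging the two V1 scans; the stated purpose of the second is repeatability. The 10-patient figure is therefore only a possibility that the plan leaves open.

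Two cautions stand. The plan links the 6.6% to control of lung inflation, so it may reflect measurement error alone. If it excludes patient-to-patient variation in true decline, then 8, 10 and 13 are all too low. The reassurance at n=20 also requires 20 patients with a 12-month MRI. No dropout rate is given for this calculation, and the standard-of-care data that Section 4 would use for patients lost to follow-up do not list MRI. As an illustration, 16 completers at an SD of 12.7% would give about 81% power.

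**Conclusion.** The concern holds. On the plan's own inputs, no form of the two-sided signed-rank test gives 90% power with 5 patients: power is zero in the exact and continuity-corrected forms and about 72% in the uncorrected form. The exact test needs 8 patients on the most favourable reading of the 6.6%, and 10 or 13 if it is the SD of a single measurement.

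The zero-power result is combinatorial and needs no distributional assumption. The figures of 72%, 8, 10 and 13 assume normally distributed changes; 10 and 13 also assume independent measurement errors.

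The practical effect is limited, because the planned 20 treated patients remain adequate for this test at all three SDs. The statement should be corrected; the design need not change.

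**What to change.** In Section 12, replace the 5-patient sentence with wording such as: *For a 10% decline at 12 months, the two-sided exact Wilcoxon signed-rank test needs 8 patients for 90% power if 6.6% is the SD of the within-patient change (power 92%).*

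In the same place:

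- State what the 6.6% measures. If it is the SD of a single measurement, give instead 13 patients with one baseline scan (SD of change 9.3%, power 93%) or 10 with the two V1 scans averaged (SD of change 8.1%, power 92%), and say which baseline value is used.
- Note that these numbers are too low if the 6.6% leaves out patient-to-patient variation in true decline.
- Optionally, add that 20 patients with a 12-month MRI keep 90% power up to an SD of the change of about 12.7%. This tells the reader more about the actual design than any minimum number does.

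The cost is a wording change. Sample, visits and analysis stay as they are.

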Using Xenon MRI to Evaluate the Efficacy of Therapies for Idiopathic Pulmonary Fibrosis

[name] – Principal Investigator
Duke University, School of Medicine
Department of Medicine
Division of Pulmonary, Allergy and Critical Care
[REDACTED]

[name] – Co Investigator
Duke University, School of Medicine
Department of Medicine
Division of Pulmonary, Allergy and Critical Care
[REDACTED]

[name] – Co Investigator
Duke University, School of Medicine
Department of Medicine
Division of Pulmonary, Allergy and Critical Care
[REDACTED]

[name] PhD – Co Investigator
Duke University, School of Medicine
Department of Radiology
[REDACTED]

[name]. – Co- Investigator
Duke University, School of Medicine
Department of Radiology
[REDACTED]

Sponsor: Genentech

NCT04071769

RESEARCH SUMMARY

1. Protocol Title: Using Xenon MRI to Evaluate the Efficacy of Therapies for Idiopathic Pulmonary Fibrosis

2. Purpose of the Study: The purpose of this PI initiated, industry sponsored study is to perform a carefully controlled study to assess if Xenon MR imaging can be used to determine treatment efficacy of Idiopathic Pulmonary Fibrosis (IPF) therapies. IPF is a devastating disease affecting more than 100,000 US residents. Patients with IPF have poor prognosis, with a mean survival time of only 35.2 months. The hallmark of the disease is a progressive process of scarring in the lung that results in thickening of the pulmonary blood-gas barrier and impaired gas exchange. In 2014, two medications became available for treatment of IPF. Over the 52 week studies, pirfenidone and nintedanib were demonstrated to slow, but not halt, the decline in lung function (as defined by reduction in forced vital capacity (FVC)) associated with progressive pulmonary fibrosis. Since delayed decline in FVC is the treatment response, it remains difficult to determine if therapies are helping an individual patient as physicians are not able to compare the individuals rate of decline off therapy. Additionally, testing new therapies for IPF require long term studies to assess changes in physiologic parameters. This makes developing potential new therapies both time and resource limited.

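### The 19 patients said to suffice for comparing pirfenidone with nintedanib match a single-group formula; two groups need 37 per drug, and 20 treated patients give about 36% power, not 90%.

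*Combined protocol and SAP*

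**What the plan says.** Section 12 bases its sample size on the spectroscopic RBC:barrier ratio. It cites early studies that "reported a variability of 6.6% in this metric", and for the treated cohort the authors "estimate that only a 10% decline will be observed at 12 months". On that basis, "requiring 90% power, would be achieved with a sample of only 5 patients".

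The section then turns to a comparison of the two drugs. It states that "we expect roughly half the patients to receive pirfenidone with the other half receiving nintedanib" and continues: "Assuming that one of the drugs reduces RBC:barrier decline to only 5% over 12 months, whereas the other yields a decline of 10" percent, "would require a sample of 19 patients, which is just achievable with the sample of 20 patients expected to be enrolled". No power is restated for this second calculation, and no formula is named for either one.

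Later in the same section the significance rule is set: "In all analyses, $P < 0.05$ (two-sided) will be considered the criterion for statistical significance". Section 4 (Design and Procedures) plans 20 subjects followed after starting therapy and 10 who do not start it. Section 2 (Purpose of the Study) describes IPF patients as having a poor prognosis, "with a mean survival time of only 35.2 months".

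**The concern.** Two questions are sized in succession. The first, whether RBC:barrier changes from baseline in one treated cohort, is a one-sample question. The second, whether the decline differs between patients on one drug and patients on the other, concerns two independent groups of about 10. The variance of a difference between two group means is twice that of one mean from a group of the same size, and the resulting n applies to each group. A single figure of 19, set against the total of 20, appears to allow for neither.

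This is the only calculation in the plan that asks for anything close to 20 treated patients, since the other asks for 5. If it is wrong, readers will credit the study with power it does not have. A non-significant between-drug result could then be read as showing that the drugs act alike, or that the metric is insensitive to treatment. The second misreading would be damaging, because whether xenon MRI can show treatment response is what the study sets out to learn.

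**Working it through.** **Inputs**
- SD: 6.6% (Section 12), taken as the SD of the percent change. The plan does not say whether it is that or the SD of one measurement.
- Significance level: two-sided 0.05 (Section 12).
- Power: 90% (Section 12), stated for the 5-patient figure and carried over to the 19.
- Effects: a 10% decline within the cohort; 10 − 5 = 5 points between drugs (Section 12).
- Group sizes: 20 treated (Section 4), split about equally, so about 10 per drug.

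**Step 1. Reproduce the plan's figures.** One-sample normal formula: n = (z₀.₉₇₅ + z₀.₉₀)² × (SD/δ)², with (1.960 + 1.282)² = 10.507.
- δ = 10: 10.507 × (6.6/10)² = 4.58, so 5. Matches.
- δ = 5: 10.507 × (6.6/5)² = 18.31, so 19. Matches.

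**Step 2. Use the formula for the comparison described.** Two-sample normal formula, n per group: 2 × 10.507 × (6.6/5)² = 36.62, so 37 per drug and 74 in total. Sizing by the t-test gives 38 per drug and 76 in total. Against a total of 19, the shortfall is about fourfold (74/19 = 3.9).

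**Step 3. Power and precision with 10 per drug, SD 6.6%.**
- Standard error of the difference: 6.6 × √(2/10) = 2.95 points.
- Noncentrality: 5/2.95 = 1.69. Two-sample t-test power is 0.361; the normal approximation gives 0.395.
- 95% CI half-width: 2.101 × 2.95 = 6.2 points, wider than the 5-point effect.
- Difference detectable with 90% power (t-test): 10.1 points.

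**Step 4. Test other readings** (t-test power for 5 points, 10 per drug unless stated).

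| Reading | Power | Comment |
|---|---|---|
| 6.6% is the SD of a change | 36% | Reproduces both 5 and 19 |
| 6.6% is the SD of one measurement; SD of change 6.6 × √2 = 9.33% (independent errors assumed) | 21% | 74 per drug needed (normal formula); CI ±8.8 points |
| SD of change 6.6/√2 = 4.67% | 62% | Gives 19 per drug, so 38 in total; the first figure would become 3, not 5 |
| One-sided test, SD 6.6% | 49% | Contradicts the two-sided rule |
| 19 meant per drug (19 v 19), SD 6.6% | 62% | Needs 38 patients; 20 are planned |

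For 10 per drug to have 90% power for 5 points, the SD of change would have to be about 3.3% (6.6 × 5/10.1), half the plan's figure.

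**Step 5. Losses before 12 months.** The calculation has no dropout allowance, and 20 against 19 tolerates one loss. Retention is not given, so the following is a range. At SD 6.6%, 9 per drug gives 33% power and 7 per drug gives 26%; at SD 9.33%, 7 per drug gives 15%. Seven per drug corresponds to constant-hazard survival with the quoted mean: exp(−12/35.2) = 0.711, or about 14 of 20. That survival model is an assumption, and the 36% in Step 3 does not depend on it.

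**The case against.** The strongest objection concerns weight. The between-drug contrast is not one of the two Specific Aims in Section 2. Section 12 tests changes from baseline with a signed-rank test and names no pirfenidone-versus-nintedanib test; treatment group enters only as something considered in the mixed models for predictors of response. Drug choice rests with the patient and pulmonologist, so the contrast is not randomised. The text also presents 20 as the expected number and checks 19 against it, so the cohort size may rest on feasibility. All of this stands, and it supports calling the contrast exploratory. It does not make the stated requirement correct.

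Some points of precision also stand. The one-sample formula is inferred, although exact agreement on both 5 and 19 makes the inference strong. The 37 comes from the normal approximation and the 36% from the t-test; the matched pairs are 37 with 40%, or 38 with 36%, and at 37 per drug t-test power is 89.5%. The 6.6% came from studies without careful control of lung inflation, so the true SD could be smaller, but it would have to halve. A constant hazard may overstate early loss in newly diagnosed outpatients, which is why retention appears only as a range. A repeated-measures model might add precision, but the plan claims no such gain and gives no correlation from which to calculate one.

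**Conclusion.** The concern holds. On the plan's own inputs (SD 6.6%, a 5-point difference, two-sided 0.05, 90% power) the comparison needs 37 patients per drug by the normal formula or 38 by t-test, not 19 in total. With about 10 per drug and no losses, t-test power is about 36%, so a true 5-point difference would be missed about two times in three. This rests on 6.6% being the SD of the percent change and on the 90% carrying over from the first calculation. Power ranges from 21% to 62% across the other SDs examined, and none brings 20 patients to 90%. The sentence is wrong as written and must be corrected.

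**What to change.** In Section 12, replace the 19-patient sentence with the two-group requirement: 37 per drug, 74 in total, by the normal formula at SD 6.6% (or 38 and 76 by t-test), naming the method and saying whether 6.6% is the SD of a change or of one measurement. State that about 10 per drug gives roughly 36% t-test power for a 5-point difference, and 90% power only for about 10 points. Describe the between-drug contrast as exploratory, to be reported as a difference with its 95% confidence interval, and say that a non-significant result will not be read as similarity of the drugs. Give the number of treated patients expected to reach V5.

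The cost is a wording change in one section. No patients, visits or procedures are added; the stated power becomes less favourable.

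### The 19 patients given for the 12-month drug comparison is a one-sample figure; two drug groups need 37 each, and the plan leaves only one patient in 20 for losses

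*Combined protocol and SAP*

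**What the plan says.** Section 12 (Data Analysis & Statistical Considerations) bases the sample size on the spectroscopic RBC:barrier ratio. The variability comes from earlier work: "Early studies, which did not control carefully for lung inflation reported a variability of 6.6% in this metric". Two calculations follow.

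- **Change within the cohort.** The investigators "estimate that only a 10% decline will be observed at 12 months", and on that basis, "requiring 90% power, would be achieved with a sample of only 5 patients".
- **Contrast between drugs.** On allocation, "we expect roughly half the patients to receive pirfenidone with the other half receiving nintedanib". The effect is then set out: "Assuming that one of the drugs reduces RBC:barrier decline to only 5% over 12 months, whereas the other yields a decline of 10" per cent. The plan concludes that this "would require a sample of 19 patients, which is just achievable with the sample of 20 patients expected to be enrolled".

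Section 4 (Design and Procedures) confirms that 20 subjects are followed after starting therapy. It plans 50 consents to reach 30 subjects, and describes the excess only in terms of screen failures. It foresees subjects lost before the last in-person visit and would use their routine clinical records; the examples listed are physical exam, vitals, PFTs and 6MWD. No rate of loss after enrolment appears anywhere.

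On prognosis, Section 2 describes patients with IPF "with a mean survival time of only 35.2 months". Section 3 puts median survival from diagnosis at under 3 years.

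**The concern.** The drug contrast compares the 12-month change in one group of patients with that in another group. Such a comparison carries the sampling error of two means, so it should need far more patients than a test of one mean against zero. Yet 19 lies close to what a one-sample formula would give.

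Separately, a requirement of 19 out of 20 at 12 months tolerates a single loss, in a disease that the protocol itself describes as rapidly fatal.

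At stake is how the 12-month drug comparison will be read. If 20 patients are thought sufficient, a non-significant difference may be taken as evidence that the drugs perform alike on this marker, when the study had little chance of showing the assumed difference.

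**Working it through.** **Inputs.** From Section 12: SD 6.6 percentage points; change of 10 points (cohort) or difference of 5 points (10 minus 5, between drugs); two-sided alpha 0.05; power 90%, written for the first calculation and assumed to carry over to the second; about equal numbers on each drug. From Section 4: 20 treated patients. From Sections 2 and 3: mean survival 35.2 months, median under 36 months.

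**Step 1. Reproduce the plan's figures.** One-sample normal formula: n = [SD × (z₀.₉₇₅ + z₀.₉₀) / δ]², with 1.960 + 1.282 = 3.242.

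- δ = 10: (6.6 × 3.242 / 10)² = 4.58, so 5.
- δ = 5: (6.6 × 3.242 / 5)² = 18.31, so 19.

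Both stated numbers come out. The one-sample t version gives 7 and 21.

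**Step 2. Use the formula that the contrast calls for.** For two groups, n per group = 2 × [SD × (z₀.₉₇₅ + z₀.₉₀) / δ]² = 2 × 18.31 = 36.6, so 37 per group and 74 in total (t-based: 38 per group). Relaxing the inputs does not recover 19: 28 per group at 80% power two-sided, and 22 per group at 80% power one-sided.

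**Step 3. Power and precision with the patients available.** Normal power = Φ(5 / [6.6 × √(2/n)] − 1.96). Half-width of the 95% CI for the difference = t × 6.6 × √(2/n).

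| Per group | Power, normal | Power, t-based | 95% CI half-width (points) |
|---|---|---|---|
| 10 | Φ(1.694 − 1.96) = 40% | 36% | 2.101 × 2.952 = ±6.2 |
| 7 | Φ(1.417 − 1.96) = 29% | 26% | 2.179 × 3.528 = ±7.7 |

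Both half-widths exceed the 5-point difference of interest.

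**Step 4. Losses.** The margin is (20 − 19)/20 = 5%. If each patient is lost independently with probability q, P(at least 19 of 20 kept) = (1 − q)²⁰ + 20q(1 − q)¹⁹:

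- q = 5%: 74%
- q = 10%: 39%
- q = 20%: 7%

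**Step 5. What the survival figures imply, as an assumption.** The documents give no 12-month survival and no survival distribution, so several shapes are shown.

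| Assumed shape | Alive at 12 months | Of 20 | P(at least 19) |
|---|---|---|---|
| Constant hazard, mean 35.2 | exp(−12/35.2) = 0.711 | 14.2 | 1% |
| Constant hazard, median 36 | 0.5^(12/36) = 0.794 | 15.9 | 6% |
| Uniform, mean 35.2 | 1 − 12/70.4 = 0.830 | 16.6 | 12% |
| Weibull, mean 35.2, shape 0.8 | 0.627 | 12.5 | 0.1% |
| Weibull, mean 35.2, shape 1.5 | 0.843 | 16.9 | 16% |
| Weibull, mean 35.2, shape 2 | 0.913 | 18.3 | 47% |

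Every expected count is below 19, and these rows count deaths alone.

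**The case against.** The strongest reply concerns attrition. A reader might infer that the protocol's own survival figure leaves about 14 patients. The documents do not support that as a finding. It needs a constant hazard applied to a mean, and other shapes with the same mean give about 12.5 to 18. The figure also describes IPF patients in general, whereas these are newly diagnosed outpatients starting treatment and screened for oxygen saturation, recent exacerbation and cardiac history. Their 12-month survival is not in the documents and could be better. This part of the objection stands, and the count can be given only as an assumed range.

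Three further points stand in part.

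- **The 90% power is written only for the 5-patient calculation.** For 19 it is implied, by the fact that the same formula and inputs reproduce the number. A reader might also infer that the whole study is underpowered. It is not so on these inputs: for the 10% cohort decline, 14 completers give Φ(10/6.6 × √14 − 1.96) = Φ(3.71), over 99.9%.
- **Unusable scans are partly covered.** Sections 4 and 9 allow scans to be repeated, and Section 6 lets a subject return after a technical cancellation. The gap is death, withdrawal and loss to follow-up.
- **The analysis softens the effect of missing visits.** Section 12 provides confidence intervals and repeated-measures models, which can use the 3- and 6-month scans. Over-interpretation of a null result is therefore a risk, not a certainty. The sample-size statement, however, is about the decline over 12 months and takes no credit for those models.

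None of this answers the first defect. The two-group shortfall is present with complete follow-up.

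**Conclusion.** The statement that 20 patients suffice for the drug contrast is wrong as written. The larger reason is the formula: 19 answers a one-group question, and the two-drug question needs 37 per group on the plan's own inputs. With 10 per group and no losses, power is about 36–40%. The second reason is that a one-patient margin is not an attrition allowance, and the fallback for lost patients does not list the xenon MRI that supplies the metric.

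This rests on reading 6.6% as the SD of the 12-month change, which the plan does not say. If it is the SD of a single measurement with independent errors (an assumption), the SD of a change is 6.6 × √2 = 9.3 and the requirement becomes 74 per group. It also assumes an even split; an uneven one lowers power further. The survivor range of 12.5 to 18 of 20 is illustrative, and the conclusion does not depend on any one value in it.

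**What to change.** In Section 12:

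1. Delete the claim that the drug contrast is within reach of 20 patients, and the figure of 19 as its requirement.
2. State an assumed range of treated patients with a 12-month scan (for example 14 to 18 of 20), and say that it is an assumption.
3. Give the two-group power or 95% CI half-width at that range. On SD 6.6% and t-based, the values lie between 26% and ±7.7 points (7 against 7) and 36% and ±6.2 points (10 against 10). The one-sample values (91% at 19, 86% at 16, 81% at 14) should not be used, since they would carry the same error forward.
4. Label the between-drug contrast descriptive, reported as an estimate with its confidence interval.
5. Say whether 6.6% is the SD of a change or of a single measurement.

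The cost is wording only, with no added enrolment and no change to visits. The downside is a less favourable stated power for the drug comparison.
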